8. ADVERSE EVENTS AND REPORTING PROCEDURES	21
8.1 Potential Adverse Events	21
8.2 Adverse Event Reporting	21
9. REGULATORY CONSIDERATIONS	21
9.1 Institutional Review of Protocol	21
9.2 Data Management Plan	21
10. Statistical Considerations and Evaluation of Results	22
10.1 Study Endpoints	22
10.2 Accrual estimates	24
10.3 Study Outcomes (ClinicalTrials.gov)	24
10.4 Analyses Plans	25
10.5 Accrual estimates	25
11. REFERENCES:	27
3.1 Inclusion Criteria	34
3.2 Exclusion Criteria	34

PROTOCOL SYNOPSIS

TITLE	Evaluation of Patients with Low-Risk and Intermediate-Risk Prostate Cancer Scheduled for High-Dose Rate Brachytherapy Using ⁶⁸ Ga-RM2 PET, ⁶⁸ Ga-PSMA-11 PET and Multi Parametric MRI
STUDY PHASE	Phase 2 study
INDICATION	Prostate cancer
INVESTIGATIONAL PRODUCTS	
⁶⁸Ga-PSMA-11; also known as:
 
 • DFKZ-11 • HBED-CC PSMA • The “Heidelberg compound” 
⁶⁸Ga-RM2; also known as:
 
 • Bombesin • BAY86-7548
SAMPLE SIZE	100 participants
PRIMARY OBJECTIVES	
To demonstrate that ⁶⁸Ga-RM2 and ⁶⁸Ga-PSMA-11 PET/MRI can detect additional cancers over mpMRI
 
To demonstrate that ⁶⁸Ga-RM2 and ⁶⁸Ga-PSMA-11 PET/MRI can assess changes in response to treatment and predict PFS at 24 months

SCHEMA

LIST OF ABBREVIATIONS AND DEFINITION OF TERMS

Ga-68; ⁶⁸ Ga	Gallium-68
IRB	Institutional Review Board
IV	Intravenous
MRI	Magnetic resonance imaging
NPV	Negative predictive value
PPV	Positive predictive value
PET	Positron emission tomography
SUV	Standardized Uptake Value
PSMA	Prostate specific membrane antigen
GRPR	Gastrin releasing peptide receptor
PRCA	Prostate cancer
HIFU	High-intensity focused ultrasound
HDR	High-dose rate

1. OBJECTIVE

Specific Aims

Aim 1: ^{68}Ga -RM2 PET/MRI and ^{68}Ga PSMA-11 PET/MRI detection of PC. We will investigate the performance of the new GRPr-binding PET radiopharmaceutical, ^{68}Ga -RM2, and compare it to the currently most widely investigated (but not FDA-approved) PC PET radiopharmaceutical, ^{68}Ga PSMA-11, as well as to mpMRI acquired during PET/MRI for the localization and staging of low-risk and intermediate-risk PC. New lesions identified on PET/MRI and not known from prior systematic prostate biopsy will be confirmed by targeted biopsy and GRPr and PSMA status will be evaluated with specific immunohistochemical stains [1, 2].

Aim 2: ^{68}Ga -RM2 PET/MRI and ^{68}Ga PSMA-11 PET/MRI prediction of PFS after local targeted therapy for PC. We will investigate if the combination of the GRPr-binding PET imaging agent, ^{68}Ga -RM2, and the most widely investigated (but not FDA-approved) PSMA-binding PET imaging agent, ^{68}Ga PSMA-11, together with mpMRI can predict PFS after local targeted therapy. We will determine if ^{68}Ga -RM2 PET/MRI and ^{68}Ga -PSMA-11 PET/MRI assessment at 6-months follow-up will predict PFS at 24 months based on standard clinical follow-up (PSA, imaging, tissue diagnosis).

2. BACKGROUND

2.1 Preliminary information

Prostate cancer (PC) remains the most-common non-cutaneous cancer diagnosed in American males, accounting for an estimated 164,690 estimated new cases and 29,430 estimated deaths in 2018 [3]. Historically, PC often presented as painful metastatic disease, and killed up to 40 per 100,000 men annually in the US between 1991 and 1993. The introduction of widespread PSA screening in the early 1990's led to a profound stage migration with most cancers detected while localized to the prostate. Subsequently PC-specific mortality dropped to 20 per 100,000 by 2012 [4]. While improvements in therapy likely play some role, independent groups in the CISNet consortium have shown through modeling that 45% - 70% of the decline in PC mortality can be plausibly attributed to PSA screening [5].

Meanwhile, PSA screening also dramatically increased detection and treatment of slow-growing, low-grade PC that would have otherwise remained asymptomatic. Treating all these cancers with radical prostatectomy or external beam radiotherapy (EBRT) is expensive to the healthcare system and led to significant short and long-term side effects in hundreds of thousands of men. As a result, despite the ~50% reduction in age-specific PC mortality in the PSA era, the US Preventive Services Task Force (USPTF) recommended in 2011 against routine screening with PSA [6] because it deemed that the harms of screening outweighed the benefits. Accordingly, PSA use and early diagnosis PC have decreased dramatically [7]. The dilemma for patients and treating physicians is: either continue screening despite the problem of overtreatment and treatment-related side effects, or do not screen and miss the opportunity for early diagnosis and cure. To reduce the harms of screening while maintaining the benefits, **there is a clear need for faster, less invasive and fundamentally less risky treatments for localized PC.**

Standard treatment options include observation, surgery (prostatectomy), radiation therapy (external beam or brachytherapy), and/or hormonal therapy, depending on the initial stage, the patient's age, co-morbidities, and preferences. If T-stage is greater than 2 or if the PSA > 20 ng/mL or if Gleason score is > 8, there is an increased risk of metastatic disease and cross-sectional imaging and bone scans are performed to identify metastases. However many cancers are diagnosed before this stage and are candidates for targeted local therapy.

Changing paradigms in management of localized PC. Not all localized PC have the same biologic

potential; most men with small, non-aggressive (Gleason 3+3) cancers can be safely followed by 'active surveillance' – a strategy that has gained acceptance in the last 5 years [8]. Low-risk PC (Gleason score ≤ 6 , pretreatment PSA level < 10 ng/mL, and clinical stage T1–T2a) is a group that accounts for 35% to 70% of all patients with PC [9, 10]. But for the remaining patients with higher grade, *clinically significant* cancers still merit treatment. They face a difficult choice: aggressive whole-gland treatment that risks life-altering side effects, vs. no treatment and the risk of cancer progression, metastasis and potential death [11]. Newer less invasive local therapies seek to offer treatment options that are faster, less invasive, less risky and potentially cheaper than surgery or EBRT. These include ablation with heating (high-intensity focused ultrasound - HIFU, microwaves, or lasers), freezing (with needle cryoprobes), electroporation, stereotactic radiation therapy and brachytherapy. Such localized therapies are becoming popular despite limited long-term evidence of tumor control, especially for ablation modalities.

The role of multi-parametric MRI (mpMRI) for guiding care. While PC is most often multifocal, the highest grade, index lesion drives clinical outcomes [12, 13]. Conventional trans-rectal ultrasound (TRUS)-guided systematic prostate biopsy consisting of 6-12 biopsy cores is limited by under-diagnosis of index lesions and over-diagnosis of small, non-aggressive tumors that pose little threat to a man's life. Use of mpMRI is increasing rapidly due to its ability to improve detection of clinically significant index tumors using MRI-guided biopsy [14]. MRI-guided biopsies find more clinically significant tumors ($\geq G7$) and less insignificant (G6) tumor than conventional systematic biopsies. MRI is increasingly used for the following:

- Prior to biopsy, MRI can be used to determine if biopsy is necessary and can enable image-targeted biopsy if an abnormality is seen on MRI [14]
- Men contemplating active surveillance: a normal mpMRI adds confidence that this is a safe management option. An abnormal mpMRI prompts a conventional MRI-transrectal ultrasound (MRI-TRUS) fusion biopsy that often reveals clinically significant cancer that warrants treatment [15].
- Men deciding between whole-gland treatment (surgery or radiation) and partial-gland focal ablation. Finding a single tumor on MRI prompts consideration of focal ablation. Finding multiple and/or bilateral tumors prompts consideration of whole-gland treatment (surgery or radiation). Finding extracapsular disease (T3 / T4) prompts workup for potential metastatic cancer.

It should be noted that mpMRI has limitations: ~20% of all index lesions are missed [16], the size of high-grade cancers is underestimated [17], and **~40% of men with a normal MRI have PC on biopsy [18]**.

Positron emission tomography (PET) and PC. PET tracers, such as ^{18}F - or ^{11}C -labeled choline and $[^{11}\text{C}]$ -acetate, are used mainly for the diagnosis of recurrent [19-21] or metastatic [22] PC. Their feasibility in primary diagnosis is limited because of uptake in benign tissue such as benign prostatic hyperplasia or inflammatory lymph nodes [23, 24]. Although choline based PET/CT is widely used outside the US for imaging PC, there have been numerous studies reporting a low sensitivity and specificity, especially at low PSA levels [25, 26]. Consequently, improved molecular imaging of PC is necessary. One novel method is PET imaging with ^{18}F -FACBC, a synthetic amino acid. Nanni et al. indicate that this tracer might be superior when compared to choline PET/CT [27]. However, others shown that ^{18}F -FACBC uptake in PC is similar to that in BPH nodules [28]. Prostate-specific membrane antigen (PSMA) is a transmembrane protein of high interest in PC. This cell surface protein is significantly overexpressed in PC cells when compared to other PSMA-expressing tissues such as kidney, proximal small intestine or salivary glands. PSMA is highly overexpressed on almost all PC [29-31]. Only 5-10% of primary PC lesions have been shown to be PSMA-negative [32, 33], making this class of radiopharmaceuticals suitable for diagnosis of primary PC and for initial staging [34-39]. Non-invasive tumor grading has also been reported [40]. PSMA ligands can be labeled with ^{68}Ga for PET imaging [41]. Experience with PET/CT using Glu-NH-CO-NH-Lys-(Ahx)- $[^{68}\text{Ga}(\text{HBED-CC})]$ (^{68}Ga -PSMA-11) indicates that this compound can detect PC relapses and metastases with high contrast by binding to the extracellular domain of PSMA,

followed by internalization [42]. Better localization of cancer within the prostate itself would also have a clinical impact by guiding image-targeted biopsy and patient selection for local targeted therapy. However, these promising agents do not detect all recurrences [43, 44] and other cancers also express PSMA [45-47]. False positive findings have also been reported using PSMA agents [48-51].

Consequently, improved imaging of PC continues to be an area of unmet clinical need. Gastrin-releasing peptide (GRP) is a 27-amino acid neuropeptide that is the mammalian homologue of the linear tetradecapeptide bombesin. It shares homology with bombesin at the C-terminal amidation sequence in the final 7 amino acids [52, 53]. The GRP receptor (GRPr) is the only well characterized receptor to which GRP and bombesin bind with a high affinity. GRPr belongs to a family of G-coupled protein receptors, and the GRP binds selectively to the GRPr [52, 53]. Studies show that GRPr is expressed at very low levels in normal prostate glands but is increased in 45-100% of human PCa [54, 55]. ⁶⁸Ga-labeled DOTA-4-amino-1-carboxymethyl-piperidine-D-Phe-Gln-Trp-Ala-Val-Gly-His-Sta-Leu-NH2 (⁶⁸Ga-RM2, formerly also known as BAY86-7548 or ⁶⁸Ga-DOTA-Bombesin) is a synthetic bombesin receptor antagonist, which targets GRPr [56]. GRPr proteins are highly overexpressed in several human tumors, including PC [57]. Because of their low expression in BPH and inflammatory prostatic tissues [58, 59], imaging of GRPr has potential advantages over current choline- and acetate-based radiotracers. Indeed, preclinical studies using BAY86-7548 have shown a high and persistent tracer uptake in mice bearing PC-3 tumor xenografts, which represent androgen-independent human PC with high GRPr expression [60]. Clinically translated GRPr antagonists PET radiopharmaceuticals include ⁶⁸Ga-RM2, ⁶⁸Ga-SB3, ⁶⁸Ga-NeoBOMB1, ¹⁸F-BAY-864367 and ⁶⁴Cu-CB-TE2A-AR06. They have been shown to have stable biodistribution in healthy volunteers [61] and mean effective doses comparable to other radiopharmaceuticals [62, 63]. Published data indicate encouraging results for use at initial diagnosis of PC [61-65] or at biochemical recurrence [66].

While the PSMA is over-expressed in prostate cancer, this is not universal; there are lesions undetected by PSMA-targeted imaging in different risk classes or stages of disease. The influence of GRPr expression on cancer grade and stage has been evaluated by several groups. Nagasaki et al. found that GRPr expression is correlated with higher Gleason score [67]. Most recently, Michaud et al. showed that ***GRPr expression in PC is independent from PSMA expression***. In some cases GRPr expression occurred in the absence of detectable PSMA expression on IHC [2].

Evolution of Radiotherapy. Localized PC is effectively treated with external beam radiation therapy (EBRT) to 78 to 80 Gy, a non-invasive, outpatient treatment regimen. It requires approximately 40 fractions, or treatments, delivered 5 days/week over 2 months, necessitating a significant time commitment from patients. Potential side effects include urinary urgency, dysuria, hematuria, urinary retention, impotence, and GI toxicity. Biochemical failure (rising PSA after treatment) may occur in as many as 20-30% of men after EBRT for intermediate risk PC [68]. Low dose rate (LDR) brachytherapy with trans-perineal radioactive seed implantation can deliver potentially higher local doses which is important for local tumor control. However, seed placement is challenging with real-time planning and seed placement resulting in variable dosimetry, and the radioactive seeds mandate contact restrictions for patients. Recently, high dose rate (HDR) brachytherapy has been utilized as an alternative. Although usually done under general anesthesia, HDR is minimally invasive, enables real time treatment planning, the ability to preferentially boost dominant tumor locations, and has favorable dosimetry [69]. Local control after HDR is excellent [70], the treatment is more convenient for patients and side effects are less common than after EBRT as the radiation is delivered with a sharp fall-off minimizing dose to surrounding pelvic structures. At Stanford, we have an active, well-established HDR brachytherapy program led by [name] who consistently treats at least 6 patients per week with this technique. Since initiation of the program approximately 3 years ago, we have treated over 500 patients with this modality either as part of a boost treatment in addition to EBRT (325 patients) or as HDR monotherapy (175 patients) for definitive treatment of their PC. These include 45 patients to date in 2018 with low or intermediate

risk PC.

Efficacy assessment: a major unsolved question. Unlike after prostatectomy, where PSA levels fall to zero soon after successful surgery, after local targeted therapy (HDR) PSA levels are poor measures of efficacy. PSA falls to a variable nadir due to continued production by residual prostate tissue as well as potential occult non-index tumor that was outside the boost region. Even the Phoenix criterion for radiation failures (2 ng/ml rise above nadir), now a *de facto* standard, has a sensitivity and specificity of only ~65% and ~77%, respectively, for clinical recurrence [71]. False negatives may occur early because it takes time for tumor to grow back fast enough to generate 2 ng/ml of PSA. False positives may be due to residual BPH, regeneration of normal prostate tissue, and prostatitis. PSA is especially problematic for ablation because some portions of the gland are left entirely untreated. The potential for residual under-treated target tumor, or occult non-target tumor to progress, and potentially become clinically significant, highlights the unmet need for sensitive surveillance methods after local targeted therapy.

Therapeutic options after local treatment. Evidence from salvage treatment for post-prostatectomy recurrence reveals that success is more likely when treatment is initiated early [72]. One theoretical advantage of local treatments is that tissue damage is restricted to the prostate. This enables options for local retreatment and second line therapy after failure. After brachytherapy, local recurrence can potentially be retreated with more brachytherapy. This ability to retreat further highlights the need for sensitive surveillance methods after initial treatment.

Can mpMRI also help find recurrence or residual tumor *after* local targeted therapy? It is much more difficult to interpret mrMRI after treatment [73]. For example, after radiation therapy, decreased exocrine function, and fibrosis can cause low signal on T2-weighted images and variable diffusion restriction that mimic tumor [74]. Similarly, after ablation, resolving hemorrhage and proteinaceous necrosis can cause variable diffusion restriction, and inflammation can cause contrast enhancement [75].

Simultaneous PET/MRI: PET/MRI is an advanced hybrid imaging technology that can provide both biological and morphological information of various biological pathways, as discussed in more details in “Approach”. Compared to PET/CT, simultaneous PET/MRI has advantages resulting from reduced radiation exposure and higher soft tissue contrast [76]. PET/MRI is particularly important for accurate localization and assessment of the pelvic extent of disease at the initial staging of PC. In fact, the majority of pathologic findings leading to up-staging are microscopic, requiring the high resolution of intraprostatic anatomy and adjacent structures afforded by co-registration with MRI rather than CT [77]. In addition, the silicon photomultipliers (SiPM) based PET detectors in SIGNA PET/MRI or digital PET/CT scanners are more sensitive than photomultiplier tubes (PMT) based PET detectors in standard PET/CT [78-80]. The knowledge we propose to acquire can be generalized to separately acquired PET/CT and mpMRI, although motion artefacts and other factors may prevent accurate fusion of the data.

In summary, some men could undergo ineffective local treatment and miss the chance for effective local salvage treatment before metastasis occurs.

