3. PARTICIPANT SELECTION AND ENROLLMENT PROCEDURES

3.1 Inclusion Criteria

- Patients must be at least 18 years of age;
- Patients must be able to provide informed consent;
- Histologically proven low-grade or intermediate-grade PC;
- Scheduled to undergo targeted local therapy (HDR brachytherapy).

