Test to be evaluated: All T1w, T2w, DWI and DCE MR images will first be analyzed and graded by two-board certified abdominal radiologists with subspecialty training in body MRI and extensive clinical experience in prostate MRI (Drs. [name] and [name]), before and after treatment. Areas of focally increased ⁶⁸Ga-RM2 or ⁶⁸Ga-PSMA-11 uptake above surrounding background on pre-therapy scans will be evaluated for changes in uptake by Drs. [name] and [name].

Hypotheses

Primary: Change in ⁶⁸Ga-RM2 or ⁶⁸Ga-PSMA-11 uptake from baseline (T0) to 6 months after start of treatment (T1) will predict treatment response better than T0-T1 changes in MRI.

Secondary: T0-T1 change in ⁶⁸Ga-RM2 or ⁶⁸Ga-PSMA-11 uptake will predict progression-free survival (PFS) better than MRI.

Statistical Analysis:

Primary: (a) logistic regression of response/non-response at T6 on T1-T0 change in PET/MRI measures; (b) McNemar tests of MRI and PET predictions of T6 response.

Secondary: (a) log-rank tests of PFS time (length of drug response) on patients dichotomized as above/below the median change in PET/MRI measures; (b) Cox proportional-hazards regressions of PFS on amount of T1-T0 change in PET/MRI measures.

Statistical Power and Sample Size: We expect a 70-80% response rate to treatment, and 20% of responders progressing by two years.

A sample size of ~75 responders and ~25 non-responders will provide 90% power at one-sided 5% error to detect sensitivity low as 80% at fixed 90% specificity, and to demonstrate a difference in sensitivities of 10 percentage points (e.g., 80% vs 90%).

Median-change groups of ~40 each among the responders will provide 90% power at one-sided 5% error to detect differences in PFS hazard ratios as small as 2.5.

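### The Aim 2 models contain only the change in uptake; without a term for tumour grade they cannot show that change adds to what is known before any scan, and may mislead if grade and change are linked

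*Combined protocol and SAP*

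**What the plan says.** **Population.** Section 3.1 admits "Histologically proven low-grade or intermediate-grade PC", with no quota or stratification by grade. Randomization (sections 2.5 and 5.2) decides only which tracer is given first.

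**Background.** Section 2.1 states that "the highest grade, index lesion drives clinical outcomes", that "GRPr expression is correlated with higher Gleason score", and, for PSMA imaging, that "Non-invasive tumor grading has also been reported".

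**Analysis.** Section 10.2 gives two primary analyses: "logistic regression of response/non-response at T6 on T1-T0 change in PET/MRI measures" and "McNemar tests of MRI and PET predictions of T6 response". The secondary analyses are a log-rank test on a split at the median change and "Cox proportional-hazards regressions of PFS on amount of T1-T0 change in PET/MRI measures". None includes, or is stratified by, grade, PSA, stage or risk group. The only adjustment named in section 10 is for clustering within patient, under Aim 1. The exploratory work on cancer subtypes is also under Aim 1 and concerns detection.

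**Hypotheses.** Both Aim 2 hypotheses are comparative: change in tracer uptake is to predict response (primary) and PFS (secondary) better than change on MRI.

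**The concern.** Grade is known before the first scan. If it is related both to outcome and to how far uptake falls, the coefficient for change mixes two things: what the scan shows and what the biopsy had already shown. The mixing can go either way.

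- If intermediate-grade tumours show a smaller fall, a small fall marks men with a worse outlook, and change looks predictive even if it carries nothing of its own.
- If intermediate-grade tumours start with more uptake and so fall further, men with a worse outlook sit in the large-fall group, and a real benefit of a large fall is diluted.

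The plan does not say whether change is absolute or relative, so neither direction can be ruled out. At stake is how Aim 2 is read. A positive result could not be separated from a better outlook in low-grade men, and a null result could be masking.

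**Working it through.** **Inputs from section 10.2.** 20% of responders progress by two years; about 75 responders, or two groups of about 40; hazard ratio (HR) 2.5; one-sided 5%; stated power 90%; about 25 non-responders in 100 men.

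**Assumptions, because the documents give no figure.** Grade HR or odds ratio (OR) 2-4, intermediate v low. Mean change differs by d = 0.25-1 SD between grade groups. The main case is a 50/50 mix. Section 2.1 puts low-risk disease at 35-70% of all prostate cancer, which would make 30-65% intermediate. That is not a figure for men scheduled for HDR, so 80% intermediate is also shown.

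**1. The plan's own PFS figure.** Expected events: 0.20 × 75 = 15 to 0.20 × 80 = 16. Events needed (Schoenfeld): 4 × (1.645 + 1.282)² / (ln 2.5)² = 41. Power with 16 events: Φ(√16/2 × ln 2.5 − 1.645) = Φ(0.19) = 57%; with 15 events, 55%. The stated 90% is not reproduced. This is a separate matter, but it sets the number of events available here.

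**2. No effect of change within grade; intermediate-grade men fall less.** With a 50/50 mix and a median split, the share of intermediate-grade men is p = Φ(d/2) in the small-fall half and 1 − p in the other. The apparent HR is roughly [1 + (HR_g − 1)p] / [1 + (HR_g − 1)(1 − p)], where HR_g is the grade HR. The rejection rate with 16 events is Φ(2 × ln HR − 1.645).

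| d (SD) | Grade HR | p | Apparent HR | Rejects |
|---|---|---|---|---|
| 0 | any | 0.50 | 1.00 | 5% |
| 0.25 | 2 | 0.55 | 1.07 | 6-7% |
| 0.25 | 4 | 0.55 | 1.13 | 8% |
| 0.5 | 2 | 0.60 | 1.14 | 8% |
| 0.5 | 4 | 0.60 | 1.27 | 12% |
| 1 | 2 | 0.69 | 1.29 | 13% |
| 1 | 4 | 0.69 | 1.60 | 24% |

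Simulation of the log-rank itself (80 men, 20% events) agrees: 7-24% at a 50/50 mix and 6-12% at 80% intermediate, against 4-6% when stratified by grade. Over mixes of 30-65% intermediate and d = 0.5-1, it gives 7-26%.

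**3. True HR of 2.5 within grade; intermediate-grade men fall more.** The apparent HR is about 2.5 divided by the factor in step 2. It runs from 2.5/1.14 = 2.19 (d = 0.5, grade HR 2) to 2.5/1.60 = 1.56 (d = 1, grade HR 4). Simulation over d = 0.5-1 at a 50/50 mix gives 1.48-2.16, with power of 20-46% unstratified against 51-57% stratified.

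**4. Logistic model (simulation; 100 men, 25% non-response, 50/50 mix, d = 0.5-1).** With no effect within grade, the unadjusted model rejects in 8-17% of trials at d = 0.5 and 14-33% at d = 1, against 4-7% adjusted. With a true OR of 2 per SD and opposing confounding, the apparent OR is 1.47-1.86. Power is 55-80% unadjusted against 86-90% adjusted.

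**5. No link between grade and change.** Stratified and unstratified log-rank tests both hold about 5%.

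**The case against.** **The link is not documented.** In context, the sentence on the index lesion says which tumour within a gland matters; it does not compare 24-month PFS in low- and intermediate-grade men. The GRPr statement concerns tissue expression, and the PSMA statement concerns imaging at one time. None concerns change. This stands. A reader might infer that the protocol itself shows grade to track the change in uptake, or that the Aim 2 estimates are biased. The documents support neither: they make distortion plausible and give no direction or size.

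**An unadjusted association is legitimate for prediction.** In step 2, change really is associated with outcome across the whole cohort, so a rejection is false only as a statement about change beyond grade. The plan's hypotheses compare PET with MRI, and the McNemar test does so within the same men. This also stands. It would be wrong to declare Aim 2 positive only if change predicts beyond risk group, because that replaces the plan's question. But the logistic, log-rank and Cox models are not within-man comparisons, and nothing in the documents says that MRI change relates to grade in the same way as PET change.

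**The cohort may be mostly intermediate.** Section 2.1 says most men with small Gleason 3+3 cancers can be followed without treatment. A lopsided mix weakens the effect, as the 80% figures show, but does not remove it.

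**The endpoints are unaffected.** Those in sections 2.5 and 10.3 count participants with assessable scans and do not depend on these models. True, but the Aim 2 hypotheses do.

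**Conclusion.** The omission is certain; its effect is conditional. As written, the Aim 2 regressions and log-rank test cannot show that change in uptake adds to the grade already known. If grade and change are linked, they may also overstate or mask the effect of change. For the log-rank, the rejection rate with no within-grade effect is about 6-24% instead of 5%, under assumed grade HRs of 2-4, shifts of 0.25-1 SD and a mix of 50-80% intermediate. In the opposite direction, power falls below the 51-57% that stratification would give. If there is no link, the log-rank loses nothing by being unstratified and stratifying leaves its error rate at about 5%. The point is worth acting on because the remedy is small and must be written down before outcomes are seen. It does not show that Aim 2 will be biased.

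**What to change.** In section 10.2:

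- Prespecify one binary factor, low v intermediate grade as documented at eligibility, and state the Gleason cut that defines it. Grade is more practical than full risk group: section 2.1 defines only low risk, and sections 6.1 and 7 do not list PSA or stage as collected items.
- Stratify the log-rank and Cox analyses by this factor and add it as a covariate in the logistic regression, for PET and MRI change alike.
- Report adjusted and unadjusted results. Base any claim of value beyond known baseline risk on the adjusted one.
- State whether change is absolute or relative, since this affects the direction of any confounding.
- Keep the PET-v-MRI hypotheses and the McNemar test as they are.

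**Cost.** A wording change, plus entering the eligibility grade in the analysis file. Statistically it takes one degree of freedom with about 15-16 expected PFS events, which leaves little room for further terms. It does not repair PFS power, which remains about 55-57% on the plan's own inputs against the stated 90%.
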